1. PROJECT TITLE

Functional Imaging of Tremor Circuits and Mechanisms of Treatment Response

4. ESTIMATED DURATION OF THE STUDY

The estimated duration of this study is 5 years for subject recruitment, fMRI testing, data analysis and publication. This protocol is being transitioned to UCSD during year 3 of 5 from the University of Miami.

5. LAY LANGUAGE SUMMARY OR SYNOPSIS (no more than one paragraph)

Essential tremor (ET) causes uncontrollable shaking, usually of the hands. Several medications are used to treat ET; however, they are often only partly effective and can have side effects that are not well tolerated. Many people with tremor have some relief from drinking alcohol. It is unclear however what brain areas produce tremors in ET and how these areas change during various activities or with medications that can suppress tremor. We plan to study the source of these tremors using functional magnetic resonance imaging (fMRI) and how tremor medications may impact the activity of various brain regions.

6. SPECIFIC AIMS

Essential Tremor (ET) is the most common tremor disorder, currently affecting an estimated 2.9 million Americans and leading to disability and decreased quality of life in 75% of cases. Tremor affects the arms disproportionately more than the head, legs, voice and face. ET may occur at any age, though prevalence increases after the age of 40. The pathophysiology of ET is poorly understood. The source of the tremor remains controversial since all studies show increased activity in the cerebellum (including mimicked tremor in controls), while animal models of ET using harmaline and a single human PET study implicate the inferior olivary nucleus in the brainstem. Treatment of ET focuses on pharmacological agents of various mechanisms (e.g. ②-blockers, anticonvulsants, benzodiazepines) and rarely deep brain stimulation of the Vim thalamus. Despite the assortment of agents used to treat ET, only ~50% of patients benefit from a particular agent. Further, their mechanisms of action on tremor are not known and systemic adverse effects are common.

Our long-term goal is to improve treatment outcomes through the development of more focused therapies for ET, while minimizing adverse effects. The goal of this proposal is to identify the brain regions and networks associated with varying ET phenotypes and delineate the mechanisms by which treatment alters aberrant activity in these networks. The central hypothesis is that blood oxygen level dependent (BOLD) functional magnetic resonance imaging (fMRI) correlates will identify the ET neural network along with mechanisms to

regulate it. Our hypothesis was formulated based on our own preliminary data using established methods as well as a novel approach we have developed. Results obtained from the proposed study will provide the critical knowledge needed to pursue targeted drug and surgical development and ultimately improve treatment of ET.

Aim 1. Does the cerebellum have increased blood flow and functional connectivity at rest? We will collect functional MRI (fMRI) data while participants are at rest and not experiencing tremor. Accelerometry will be used to confirm that no tremors occurred during data acquisition. We will utilize our Context Differential Autocorrelation Mapping (CDAM) method to compare global functional connectivity in a group of subjects with ET to a group of age-matched controls. We hypothesize that the inferior olive, cerebellum, and red nucleus (Mollaret's triangle) will have significantly greater functional connectivity in the ET group compared with controls.

Aim 2. Are postural and kinetic tremors associated with different aberrant networks? We will collect fMRI data while ET subjects perform two separate tasks. During one task, subjects will be verbally cued to elevate their arm in a tonic position to manifest postural tremor during fMRI data acquisition, in a block-design paradigm. Accelerometry will be used to quantify the frequency and severity of the postural tremor. During a second task, subjects will be similarly cued to draw an Archimedes spiral to elicit kinetic tremor. Tablet drawings will be digitized to quantify the frequency and severity of the kinetic tremor. We will use established fMRI analysis methods to generate statistical parametric maps (SPMs) and CDAM to compare the regional differences in activation and connectivity between postural and kinetic tremor. We hypothesize that postural tremor will be associated with greater inferior olive activation and connectivity, while kinetic tremor will have greater cerebellar activation and connectivity.

Aim 3. What regulatory changes in the tremor networks occur to explain the tremor-suppression effects of ethanol and propranolol? Using the resting, postural, and kinetic paradigms in Aims 1 and 2, we will assess the fMRI-based activation and connectivity changes for all ET subjects under three conditions: baseline (no drug), acute ethanol (50ml of 40%EtOH) challenge, and stable dose of propranolol. We will assess the regional activation and functional connectivity responses for each condition using SPM and CDAM methods. We hypothesize that ethanol's mechanism of tremor suppression is by reduction of olivo-cerebellar connectivity, while propranolol acts to reduce inferior olive activation.

With respect to expected outcomes, the findings of aims 1-3 are expected to identify the neuroanatomical correlates of ET, with particular attention to the defining characteristics of postural and kinetic tremors of ET, and the underlying mechanisms of action on the structures identified of two existing agents with known efficacy. The knowledge gained by this work will have direct applicability to the development of: novel pharmacological agents and surgical devices with the aid of a neuroimaging biomarker. In addition, these findings stand to impact clinical management by providing information that can be used to tailor treatment to individual patient characteristics, thereby avoiding the trial-and-error methods currently used to guide agent selection (e.g. if $\mathbb Q$ -blockers are found to act more effectively on a site associated with postural tremor). In addition, we plan to collect DNA samples on this rich dataset for future imaging-genomics studies.

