
After completion of the screening visit, subjects will be scheduled for the fMRI visit that will last no more than 2-hours. Subjects will be asked to lie still for up to 15 minutes at a time. An accelerometer device will be placed on the hand to measure movement. We will use fMRI to observe the brain's activity during three (3) different activities: arms resting by the side, right arm elevated and maintained in the air, and while drawing a spiral with the right hand. These tasks will be performed multiple times during 5-minute runs.

At the completion of study participation, subjects will receive payment for their participation. Payments for incomplete participation will be prorated based on consent form guidelines.

ET Volunteer Study Procedures

SCREENING

Subjects will be screened for eligibility and after providing informed consent, PI will conduct an examination to confirm the diagnosis of Essential Tremor (ET) and to exclude any other neurologic disorder. PI will obtain medical history, and a videotaped neurological exam that will include the following assessments: United Parkinson's Disease Rating Scale (UPDRS), Essential Tremor Rating Assessment (TETRAS), Montreal Cognitive Assessment (MOCA), Scale for the Assessment and Rating of Ataxia (SARA), baseline Spirography and Accelerometry. A urine pregnancy test will be performed on female participants of childbearing potential.

VIDEO RECORDING

As part of the evaluation, a video recording will be collected to document exam findings. Participants decide whether these videos may be used solely by the research team for this research project, or additionally may be used for other purposes such as educational or scientific meetings.

BLOOD SPECIMEN COLLECTION

As a part of the screening visit, participants will be requested to provide a blood sample that will be used for future genetic research on ET and related disorders. The total amount of blood removed will not exceed 20 ml (4 teaspoons).

MEDICATION TAPER

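### Aim 2's contrast of postural with kinetic tremor within ET subjects cannot be separated from holding versus drawing, and the controls' runs of the same tasks have no stated role

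*Combined protocol and SAP*

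**What the plan says.** Section 6, Aim 2, asks whether postural and kinetic tremor arise from different abnormal networks. It describes the data as follows: "We will collect fMRI data while ET subjects perform two separate tasks". One task is sustained arm elevation, for postural tremor. The other is drawing an Archimedes spiral, for kinetic tremor. The analysis, by statistical parametric maps and the CDAM connectivity method, is to "compare the regional differences in activation and connectivity between postural and kinetic tremor". The hypothesis has two parts: more inferior olive involvement in postural tremor, while "kinetic tremor will have greater cerebellar activation and connectivity".

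Tremor is measured in both tasks, with different instruments: "Accelerometry will be used to quantify the frequency and severity of the postural tremor" and "Tablet drawings will be digitized to quantify the frequency and severity of the kinetic tremor". No role for these measures in the imaging model is given.

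Controls have a stated analytic use only in Aim 1, at rest, where the plan is to "compare global functional connectivity in a group of subjects with ET to a group of age-matched controls". Yet section 9, Healthy Volunteer Study Procedures, has controls scanned during the same three activities as ET subjects: "arms resting by the side, right arm elevated and maintained in the air, and while drawing a spiral with the right hand". The text available for this review does not say how the controls' posture and spiral runs enter Aim 2.

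**The concern.** Drawing a spiral and holding an arm still are different movements, and brain activity can differ between them in anyone. If each tremor type is observed under only one of them, and only in people with tremor, the data cannot say whether a regional difference belongs to the tremor or to the task. More runs, or subtracting rest, do not change this.

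The cerebellar half of the hypothesis is the exposed part. The opening of section 6 says that "all studies show increased activity in the cerebellum (including mimicked tremor in controls". Cerebellar activity during movement is therefore not in itself evidence of an abnormal network. Followed as written, Aim 2 could report a kinetic tremor network in the cerebellum that is only the normal difference between drawing and holding.

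Section 7 makes the question of separate networks one of the study's goals, and the expected outcomes in section 6 look to the findings to help tailor treatment.

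**Working it through.** The plan gives no power, alpha or effect size for Aim 2, so there is no figure to reproduce. The check covers estimability and then size.

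**Inputs from the protocol.** 55 ET subjects and 33 controls (section 10; 55 + 33 = 88, as stated). One task per tremor type (section 6, Aim 2). The same tasks in controls (section 9).

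**Assumptions.** Two-sided 5% tests and 80% power; one test per region with no whole-brain correction; all 88 subjects evaluable; effects in units of the SD of the within-person spiral-minus-posture difference, equal in both groups.

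**1. Estimability.** Let H and D be the ordinary effects of holding and drawing relative to rest, and P and K the added effects of postural and kinetic tremor.
- ET, spiral minus posture: (D − H) + (K − P)
- Controls, spiral minus posture: D − H
- ET minus controls: K − P

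With ET subjects alone, three cell means (rest, hold, draw) must carry five parameters (intercept, H, D, P, K). The design has rank 3 of 5 and K − P is not estimable. Adding the control cells and a group term gives rank 6 of 6, and K − P is estimable as the group-by-task interaction, provided D − H is the same in both groups.

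**2. False cerebellar findings with K − P = 0.** The ET-only paired test has noncentrality d × √55 = 7.416d on 54 df. The group-by-task column assumes an equal task effect in both groups.

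| Task difference d | Noncentrality | ET-only test rejects | Group-by-task test rejects |
|---|---|---|---|
| 0.2 SD | 1.483 | 30.8% | about 5% |
| 0.3 SD | 2.225 | 58.9% | about 5% |
| 0.5 SD | 3.708 | 95.4% | about 5% |

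**3. False support for the whole hypothesis.** Suppose only the cerebellum has a task effect. The olive must then also be significant in the predicted direction by chance, with probability 0.025. If the regions are uncorrelated, the product is 0.308 × 0.025 = 0.008, 0.589 × 0.025 = 0.015, or 0.954 × 0.025 = 0.024. Simulation gives 0.008, 0.015 and 0.023, and 0.001, 0.004 and 0.019 at correlation 0.5.

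**4. Precision of the alternative.**
- Standard errors: ET-only 1/√55 = 0.135; group-by-task √(1/55 + 1/33) = 0.220, on 86 df.
- Detectable with 80% power, normal approximation: (1.960 + 0.842) × 0.135 = 0.378 and 2.802 × 0.220 = 0.617. Exact noncentral t: 0.385 and 0.624 SD.
- Power of the group-by-task test in one region: 43.5% at 0.4 SD, 61.2% at 0.5 SD, 76.9% at 0.6 SD.
- Both parts at 0.5 SD: 0.612² = 0.375 if the regional contrasts are uncorrelated (simulated 0.374); 0.302 at correlation 0.5. The two parts predict opposite signs, so positive correlation lowers joint power.
- Both parts reach 80% at 0.715 SD (uncorrelated) or about 0.72 SD (correlation 0.5).
- If activation and connectivity are each tested at 2.5%, power at 0.5 SD is 49.8% for one region and 0.498² = 24.8% for both parts, uncorrelated.

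**5. When the equal-task-effect condition fails.** If the controls' task effect is half that of ET subjects for reasons other than tremor, the residual differences are 0.1, 0.15 and 0.25 SD. The group-by-task test then rejects in 7.3%, 10.3% and 20.2%.

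**The case against.** The strongest reply is that the design already holds the remedy. Controls perform both tasks, calling a network aberrant implies a normal reference, and a one-paragraph aim need not list every contrast. On that reading the plan lacks a sentence, not a method. It stands to the extent that a control comparison may well have been intended and that the gap is not in data collection. But the contrast that is written down is within ET subjects, and asking about aberrant networks is a reason to state the normal reference rather than leave it implied.

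Further points:
- A second task of each type would not help, because section 7 defines the tremor types by the activity: kinetic tremor needs movement and postural tremor needs a held posture. This stands, and it is why the remedy lies in the control runs.
- The two-part hypothesis gives protection. This stands for the full crossover (under 3%), but not for a cerebellar finding reported alone.
- The rejection rates are simply the power of a paired test at chosen effect sizes. That is true; they show how readily an ordinary task difference would be detected, not how large it is.
- Mimicked tremor is not the same as drawing versus holding. This also stands in part. It shows that cerebellar activity is not specific to ET, but it equally marks a limit of the proposed contrast.
- Aim 3 varies tremor while the task is constant, by repeating the tasks after ethanol and on propranolol. There, however, tremor change is mixed with drug effect.

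**Conclusion.** The concern holds. As stated, the Aim 2 contrast cannot distinguish a difference between tremor networks from an ordinary difference between drawing and holding, and nothing in the available text brings the controls' task runs into it. That aliasing follows from the design and needs no assumption. Its size does: under the stated assumptions, an ordinary cerebellar task difference of 0.2 to 0.5 SD would be taken for a tremor effect in about 31% to 95% of trials. The exposure is to the cerebellar claim, not to the full crossover. It should be fixed before analysis. Some pages were absent from the text reviewed, so the finding on the controls' role is limited to what was supplied.

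**What to change.** Add to Aim 2 a statement such as: *Any conclusion that postural and kinetic tremor have different abnormal networks rests on the group-by-task contrast, (spiral minus posture in ET, no-drug baseline runs) minus (spiral minus posture in controls), in the hypothesised inferior olive and cerebellum regions. The ET-only contrast is also reported but does not by itself support that conclusion.*

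Association between subjects of activation with tremor severity within each task (accelerometer for posture, tablet for spiral) can be supportive, because the task is then constant. A site covariate is an optional minor addition.

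State the limits too. The contrast does not remove movement or sensory feedback produced by the tremor itself, or group differences in how the tasks are performed.

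**Cost.** No new scans are needed, since the control runs are already scheduled. Section 10 counts 27 of 88 subjects as completed, leaving 88 − 27 = 61 to enrol, so the rule can be set before most data exist. The price is precision: at a tremor-specific difference of 0.5 SD, power is about 61% for one region and 30% to 37% for both parts together. The crossover claim may have to be reported as unresolved, and the plan should say so in advance.

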A tremor medication consultation will be conducted with the PI reviewing the medication history. Participants taking no medications for ET will proceed to be randomized to one of the two fMRI visits (A or B). If a subject is on tremor medications and gives consent to participate in this study, tremor medications will need to be discontinued. This plan may be carried out by either the subject's primary physician or study PI in consultation with the Safety Advisory Committee (see section 14), depending on preference of subject and

treating physician. If subject has a treating physician, the PI will contact the physician to discuss whether there are any potential safety concerns with tapering tremor medications and review the plan to taper/titrate medications; taper will only occur with physician approval. The duration of the medication taper prior to MRI visit A depends on the type of tremor medication the subject is on with the period being at least five half-lives. In terms of the period between MRIs, this may be as short as two weeks and up to several months, though no explicit time limitations are set. The duration depends upon the time needed for a subject to taper off all tremor medications for MRI visit A, and the time necessary to reach a steady state of propranolol SR for MRI visit B. If a subject cannot tolerate the medication taper (e.g. worsening tremors create undo disability or the presence of an unexpected adverse effect), the PI will consult with the Safety Advisory Committee and discuss restarting medications with subject and treating physician (if present) and subject will be withdrawn from the study.

FUNCTIONAL MRI (FMRI) OVERVIEW

After completion of the screening visit, subjects will be scheduled for the fMRI visit that will also last approximately 2-hours. Women of childbearing potential will undergo a second urine pregnancy test prior to MRI visit A. ET participants already on stable doses of Propranolol SR will first undergo fMRI on Propranolol SR. Participants taking no medications for ET will be randomized to one of the two fMRI visits (A or B). After completion of one, participants will undergo the other visit type.

FMRI VISIT A

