During this visit, subjects will remain off tremor medications for a set period of time. The PI will provide specific instructions about how to do this since it varies based on the individual subject's medication history. Women of childbearing potential will undergo a second urine pregnancy test prior to MRI. During this visit, subject will be asked to perform three different activities: arms resting by the side, right arm elevated and maintained in the air, and while drawing a spiral with the right hand. Subject will perform these tasks multiple times during 5-minute runs. PI will then provide subject with a single 50-ml serving (1 shot) of 40% ethanol to drink and a high resolution structural MRI is performed, during which time the tremor suppression effects will begin. The same tasks performed during the first half of the study will be repeated. PI will complete an Alcohol intoxication Scale at the onset of the visit and again after MRI to ensure subjects are not intoxicated upon discharge. Subjects who demonstrate signs of intoxication will be monitored until they are back to their baselines.

FMRI VISIT B

During this visit, we will study how the brain and tremors respond to propranolol SR (Inderal LA). Before participating in this visit, subjects will need to be on a stable dose of this medication. In order to accomplish this, the subject will receive detailed instructions from PI on how to start and increase the medicine in consultation with the treating physician and/or Safety Advisory Committee. Subject responses to medication (benefits and adverse effects) will be monitored through weekly telephone calls. Once a stable dose of medication has been achieved, the subject will be scheduled for the fMRI scan. During this visit, the subject will be asked to perform three different activities: arms resting by the side, right arm elevated and maintained in the air, and while drawing a spiral with the right hand. At the completion of the visit, the study investigator will instruct the subject on how to taper off this medicine based on consultation with the treating physician and/or Safety Advisory Committee.

STUDY COMPLETION

Three (3) scenarios exist for study completion/termination:

1) Premature termination prior to completion of all visits

In this scenario, the subject will return to their baseline medications under the direction of their treating

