19. EXPENSE TO PARTICIPANT

The only expense to the participant is medication related. At least 30% of ET subjects enrolled into this study are already taking Inderal LA or the equivalent Propranolol SR. We have evaluated the viability of supplying all participants with study-sponsored drug but that solution was not financially viable. Some of the individuals coming into the study may be on the brandname Inderal LA while others may be on the generic Propranolol SR. The cost of the brandname is prohibitive and these added costs were not budgeted nor approved by NIH.

Additionally, it would be unethical to switch formulations on a patient who is comfortably taking the brand name because it would be cost effective to us. Therefore, the most viable option would be to have subjects purchase the medication, brand or generic, retain their receipts and provide them to the study coordinator. We will reasonably reimburse subjects for the cost of their medication.

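### As described, Aim 3's ethanol contrast cannot be separated from time in session, so it cannot by itself show ethanol's mechanism; the propranolol contrast has a smaller, correctable visit-order problem

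*Combined protocol and SAP*

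**What the plan says.** Section 6, Aim 3, compares ET patients under no drug, acute ethanol and a stable dose of propranolol. It hypothesises that ethanol's "mechanism of tremor suppression is by reduction of olivo-cerebellar connectivity", and that propranolol reduces inferior olive activation. The expected outcomes in the same section include the "underlying mechanisms of action on the structures identified of two existing agents with known efficacy".

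Section 9, fMRI Visit A, gives one sequence for all ET patients. They first do the rest, posture and spiral tasks off tremor medication: "Subject will perform these tasks multiple times during 5-minute runs". They then take the ethanol drink and have a structural scan. After that: "The same tasks performed during the first half of the study will be repeated".

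Visit B describes the three tasks on propranolol. For healthy volunteers, section 9 says "These tasks will be performed multiple times during 5-minute runs". Neither visit is described as having an interval followed by a second set of runs.

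On visit order, section 9 (Functional MRI Overview) says: "ET participants already on stable doses of Propranolol SR will first undergo fMRI on Propranolol SR". Patients on no ET medication are randomised to have Visit A or Visit B first. No explicit first-visit rule is given for patients on other tremor drugs. Section 19 states: "At least 30% of ET subjects enrolled into this study are already taking Inderal LA" or its generic equivalent.

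**The concern.** The ethanol effect is estimated as the second half of Visit A minus the first half. Anything else that changes over the session (fatigue, habituation, scanner drift, practice at the spiral) falls into the same difference. With no described set of runs that is late in the session and free of ethanol, the two explanations predict the same data. A fall in olivo-cerebellar connectivity would fit the Aim 3 hypothesis, but it would equally fit a time effect in that pathway. What is at stake is the step from change to mechanism.

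The propranolol comparison is between visits, so its exposure is to visit order. Order is fixed for existing users and randomised only for unmedicated patients. A pooled contrast that ignores order would absorb part of any first-to-second-visit change, which could partly mimic or mask a fall in olive activation.

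**Working it through.** The text available gives no significance level, power, effect size or SD for Aim 3, so there is no planned figure to reproduce. The main check is whether the ethanol effect is identifiable.

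**1. Ethanol against time in session.** The cells below are those described in section 9.

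| Cell | Intercept | ET | Late half | Ethanol | Propranolol |
|---|---|---|---|---|---|
| ET, Visit A, first half | 1 | 1 | 0 | 0 | 0 |
| ET, Visit A, second half | 1 | 1 | 1 | 1 | 0 |
| ET, Visit B | 1 | 1 | 0 | 0 | 1 |
| Control visit | 1 | 0 | 0 | 0 | 0 |

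The late-half and ethanol columns are identical. The matrix has rank 4 for 5 parameters, so the ethanol effect is not estimable alongside a free time effect. Adding a late no-drug control cell (1, 0, 1, 0, 0) raises the rank to 5 of 5. Ethanol then becomes estimable, provided that ET patients and controls share the time effect.

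**2. What an unrecognised drift would do.** This is an illustration, since the documents give no drift size. Assume no ethanol effect, one region, a paired two-sided t-test, n = 55 (section 10), and a drift d in SDs of the paired change. The noncentrality is d√55.

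| d | d√55 | Rejection at assumed 0.05 | Rejection at assumed 0.001 |
|---|---|---|---|
| 0.2 | 1.48 | 31% | 3% |
| 0.3 | 2.22 | 59% | 12% |
| 0.5 | 3.71 | 95% | 59% |

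**3. Propranolol and visit order.** Let P be the share scanned at Visit B first. A change v from first to second visit enters propranolol-minus-baseline as +v when A is first and −v when B is first. The pooled contrast therefore carries (1−P)v − Pv = (1−2P)v. Let p be existing propranolol users (B first) and u unmedicated patients (randomised, taken as 1:1), with the rest assumed A first. Then P = p + u/2 and the residual is 1 − 2p − u.

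- p = 30%, u = 70%: 1 − 0.60 − 0.70 = −0.30
- p = 30%, u = 40%: 1 − 0.60 − 0.40 = 0
- p = 60%, u = 40%: 1 − 1.20 − 0.40 = −0.60

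The 30% is the floor in section 19. The other shares are assumptions.

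**4. Precision after adjusting for order.** Fit prior-treatment stratum means plus order, with unit SD of the paired change. Order is then estimated only in the randomised stratum of size n_u. With b patients fixed B first and a fixed A first,

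SE = √[1/55 + ((b − a)/55)² / n_u].

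- 38 unmedicated, 17 propranolol, 0 other: √[0.01818 + (17/55)²/38] = 0.144
- 22, 17, 16: √[0.01818 + (1/55)²/22] = 0.135
- 22, 33, 0: √[0.01818 + (33/55)²/22] = 0.186

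The unadjusted SE is 1/√55 = 0.135.

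**The case against.** The Aim 3 wording is a hypothesis and the mechanism statement is an expected outcome. A reader might infer that the plan contains a rule converting any post-ethanol change into a mechanism. It does not. The quotes show the intended inference, which is why the remedy is to limit the conclusion.

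A reader might also infer that late no-drug runs in controls are ruled out. They are not. Section 9 gives controls repeated runs in a visit of up to 2 hours and does not set out their layout. What stands is that no such set is described.

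It could be argued that repeated runs allow a drift correction. Within the no-drug half this works only by extrapolating past the drink under an assumed shape. With linear drift, k runs per half and a gap of g run lengths, the variance of the ethanol estimate is multiplied by 1 + 3(k+g)²/(k²−1). For an assumed 2 to 4 runs and a gap of 0 to 2, this ranges from 4.2 (k=4, g=0) to 17 (k=2, g=2). The text describes no such correction, and it would be a weak safeguard.

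Drift may be small, and to support the hypothesis it would have to lower olivo-cerebellar connectivity in particular. That is fair. A change confined to the hypothesised pathway would be partial evidence for ethanol, but it would not remove the confounding. It is also tempting to say that connectivity measures are more exposed to drift than block-design activation. Nothing in the documents supports that ranking, and the point does not need it.

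**Conclusion.** The main point holds. In the design as described, ethanol and the second half of Visit A are completely confounded, so the ethanol contrast cannot by itself support a statement about mechanism. This follows from the sequence alone and needs no assumed number. The rejection rates show only what a drift of a given size would do. They are not evidence that drift exists or that an ethanol finding would be false.

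The propranolol point is secondary and modest. A reader might infer that propranolol is confounded in the same way. It is not, because order is randomised among unmedicated patients and can be separated from the drug there. Under the assumed mixes, the unadjusted contrast carries −0.30, 0 or −0.60 of any visit effect, so it can be unaffected. More extreme values would need, for example, every ET patient to be an existing propranolol user, which sits badly with a protocol that provides for unmedicated patients.

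**What to change.** **1. Ethanol.** In Aim 3 and the expected outcomes, state that the ethanol contrast as described is not separable from time in session. Limit the conclusion to change after ethanol rather than ethanol's mechanism, unless no-drug runs at the matching interval are available from controls. Even then, say that the correction assumes ET patients and controls share the drift. The cost is wording and a narrower claim.

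**2. Propranolol.** In the propranolol-versus-baseline analysis, include visit order and prior-treatment stratum (propranolol, other tremor drug, none). Report the order that other-drug patients had, and show the randomised unmedicated stratum separately. The adjustment assumes the same visit effect in all strata, and it cannot be fitted if no patient is unmedicated and order follows prior treatment. The cost is some precision: an SE of 0.135 to 0.186 SD against 0.135 unadjusted, under the assumed mixes.

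**Optional, not part of the required fix.** Imaging change could be related to recorded tremor change as a supportive analysis. No-drug repeat runs could be added in the remaining controls if the 2-hour visit allows. By the counts in sections 8 and 10, completers are 22 − 2 = 20 ET patients and 8 − 1 = 7 controls, which leaves 35 ET patients and 26 controls at UCSD. With equal SDs of change, that comparison has SE √(1/35 + 1/26) = 0.259 SD, against 1/√35 = 0.169 SD for the raw contrast in the same 35.
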